#### Columbia Suicide Severity Rating Scale (C-SSRS)

The number and percentage of subjects with suicidal ideation or suicidal behavior based on the C-SSRS will be summarized by treatment group. Suicidal ideation or behavior are defined as:

- Suicidal ideation: A "yes" answer at any time during treatment to any one of the five suicidal ideation questions (Categories 1-5)
- Suicidal behavior: A "yes" answer at any time during treatment to any one of the five suicidal behavior questions (Categories 6-10)
- Suicidal ideation or behavior: A "yes" answer at any time during treatment to any one of the ten suicidal ideation and behavior questions (Categories 1-10)

The intensity of most severe suicidal ideation during the subject's lifetime, during the double-blind treatment period, and during the safety follow-up period will also be presented by treatment group for the SAF. Intensity of most severe ideation is a sum of the 5 intensity items (Frequency, Duration, Controllability, Deterrents, and Reasons for Ideation).

Actual lethality and potential lethality on most lethal attempt will also be summarized by treatment group.

Supportive listings will be provided and will include the subject number, study center number, lifetime history, and post-baseline values. Intensity of suicidal ideation, suicidal behavior type, and lethality of suicidal behavior will also be included in these listings.

A listing of all AEs occurring in subjects who have suicidal ideation or suicidal behavior will also be provided.

#### Cardiac Assessments

A 12-lead ECG will be performed prior to the administration of study drug at the timepoints of assessments.

The Investigator will enter a signed and dated clinical interpretation of the ECG trace in the eCRF. At each timepoint, absolute values and change from Baseline of ECG numeric variables will be summarised through descriptive statistics. The number of available observations and the number of

normal, abnormal clinically significant and abnormal not clinically significant values (absolute and in percentage) will be presented.

Shift tables showing the number of subjects who shifted from normal, abnormal not clinically significant or abnormal clinically significant at baseline to normal, abnormal not clinically significant or abnormal clinically significant at each post-baseline time of assessment will be presented.

#### 8.5 Plasma Biomarkers and Pharmacokinetic Analysis

Biomarkers, including GFAP, NFL and potentially TDP43, will be summarized descriptively for SAF.

Plasma concentration-time data for buntanetap will be listed and summarized descriptively (number of subjects (N), mean, geometric mean, median, SD, coefficients of variation (CV), minimum, and maximum) for the SAF.

Non-compartmental analysis of one analyte (buntanetap) in blood matrix concentrations will be performed using validated computer software Phoenix. Results will be tabulated and graphically displayed using Phoenix and appropriately interpreted by a PK Scientist. Calculations will be based on the actual sampling times recorded during the study. The following PK parameters will minimally be determined, as data permit:

- Area under the curve (AUC), including AUC0-10hr and AUC0-inf
- Maximum concentration (Cmax) and time of maximum concentration (Tmax)
- Terminal half-life (t/2)
- Systemic clearance (CL).

#### 8.6 Multicenter Studies

No per-center analyses are planned.

#### 8.7 Adjustment for Covariates

Baseline value will be used as a covariate in the MMRM analyses for the primary efficacy endpoint (see Section 8.3.7).

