6.1. Randomization

Subjects who have signed an informed consent and meet screening eligibility requirements will be randomly assigned to the active and placebo treatment groups at 1:1:1 ratio.

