7.8.2. Permitted Concomitant Medications

This protocol allows concomitant treatment with anti-parkinsonian medications at stable doses for 4 weeks or greater prior to screening.

Use of the following medications is allowed only if the patients have been stable on them for at least 4 weeks before screening and will continue to be stable throughout the study:

- tricyclic antidepressants
- antipsychotics prescribed for any reason. However, the prescribed dose must be equal to or less than the following doses for each listed medication: quetiapine 50 mg/day, risperidone 1.5 mg/day, olanzapine 5 mg/day, aripiprazole 10 mg/day. If the subject is on other antipsychotics besides the ones mentioned above, please consult the MM before screening the subject.
- psychostimulants

Discontinuation and/or change of any of the above medication during the study is discouraged and should consult with the Medical Director and Sponsor for further guidance.

If subjects are taking any anticonvulsant medications used for epilepsy or mood stabilization, neuropathic pain indications, dosing must be stable for at least 4 weeks prior to screening.

Mood-stabilizing psychotropic agents, including but not limited to lithium, are allowed. Dosing must be stable for at least 4 weeks prior to Screening.

Use of short acting benzodiazepines and hypnotics for treatment on an as-needed basis for insomnia or daily dosing as anxiolytics is permitted but should be avoided for 8 hours before administration of cognitive tests. If sedating medication is given for any short-term use, then all cognitive assessments must be administered at least 24 hours after administration of the sedative.

At this time, there is no controlled clinical data available for anyone receiving SARS-CoV-2 (COVID19) vaccination while being treated with buntanetap. However, based on the intended mechanism of actions and currently available data for these vaccine candidates and for buntanetap, it is not believed that there are specific risks to consider in subjects participating in this study who have received SARS-CoV-2 (COVID19) vaccination or who are planning to receive the vaccination. As such, SARS-CoV-2 (COVID-19) vaccination is not prohibited.

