 - Oral, intravaginal, or transdermal combined (estrogen plus progestogen) hormonal contraception associated with inhibition of ovulation
 - Oral, injectable, or implantable progestogen-only hormonal contraception associated with inhibition of ovulation
 - Intrauterine device (IUD)
 - Intrauterine hormone-releasing system (IUS)
 - Bilateral tubal occlusion
7. General cognition and functional performance sufficiently preserved that the subject can provide written informed consent.
8. No evidence of current suicidal ideation or previous suicide attempt in the past month as evaluated in the Columbia Suicide Severity Rating Scale.
9. Stability of permitted medications prior to screening for at least 4 weeks.
10. At screening subjects do not need to but may be on the following medication:
 - Standard of Care anti-parkinsonian medication
 - Anticonvulsant medications used for epilepsy or mood stabilization, neuropathic pain indications
 - Mood-stabilizing psychotropic agents, including, but not limited to, lithium.
11. Adequate visual and hearing ability (physical ability to perform all the study assessments).
12. Good general health with no disease expected to interfere with the study.
13. Subjects previously exposed to buntanetap can still be included in the study after a 28- day wash out period.

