9.2. Baseline Visit

Baseline procedures include functional, cognitive, and behavioral assessments, safety assessments, and review of concurrent medications and potential adverse events that might occur. Fasting is required for safety laboratory tests. Participants should stop all Parkinson's disease SOC 12 hours prior to the visit to ensure a clinical OFF-state. For patients who are not on any Parkinson's disease SOC, their natural state will be considered OFF-state and since they won't have ON-state, it should be documented accordingly in the source documents.

Baseline visit should be completed in one day except for the intense PK sub-group.

Day 1:

Subjects should arrive fasted in the morning after an overnight fast. Clinical safety labs will be drawn and sent to the central lab for analysis.

After safety lab, patients will be provided low-fat light meal before completing functional and cognitive evaluations (completed in an OFF state after holding PD meds for 12 hours prior to arrival at site), a physical and neurological exam, collecting vital signs, ECG, and reviewing and recording adverse events and concurrent medications. Sites should take detailed notes of contents of all meals provided to the patients. Following completion of all these procedures, subjects who continue to meet all protocol inclusion criteria and no exclusion criteria should be randomized. Patients can take their SOC medication at this point if needed.

For sparse PK group (i.e. any subject that is not participating in the intense PK sub-study), if no medical or compliance concerns are identified, the subject will move on to the PK sampling phase, which will entail the following procedures:

- 1) Collect initial samples of blood (hour 0) with venipuncture unless PI deems inappropriate.
- 2) Administer first dose of assigned study drug after the hour 0 sampling.
- 3) Collect blood (10mL) at the 1.5hr timepoint. Blood should be taken within \pm 10 mins of times.
- 4) Perform the final safety monitoring.

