## 8.3.7 Primary Analysis

The primary efficacy endpoint in this clinical trial is the change from baseline to Month 6 in the score for MDS-UPDRS part II (OFF-state) between each of the two regimens of buntanetap and Placebo.

The statistical hypothesis to be tested for primary efficacy is described as:

• Null Hypothesis (H0):

The difference in change in MDS-UPDRS Part II (OFF-state) scores from Baseline to Month 6, between treatment (active vs placebo) regimen = 0.

• Alternative Hypothesis (H1):

The difference in change in MDS-UPDRS Part II (OFF-state) scores from Baseline to Month 6, between treatment (active vs placebo) regimen  $\neq$  0.

The primary endpoint will be analyzed via MMRM. The model will include treatment, timepoint, treatment-by-timepoint interaction as the fixed effects and baseline as the covariate. The variance-covariance matrix will be assumed to be unstructured.

This analysis will be conducted after all subjects have reached Month 6 or early withdrawal, whichever comes first. The primary analysis will be conducted in ITT. The mITT and PPS will be used to support the primary analysis.

Descriptive statistics per visit and change from baseline for each visit will be provided.

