#### 8.8 Examination of Subgroups

No subgroup analyses are planned for this study.

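### Whether a subject takes anti-parkinsonian medication is known before randomization and changes what an OFF-state score measures, yet neither the MMRM nor any planned efficacy display uses it; adding it is a free, modest improvement

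*SAP*

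**What the plan says.** Background therapy is optional. Protocol 8.1 introduces standard-of-care anti-parkinsonian drugs with "At screening subjects do not need to but may be on the following medication", and Protocol 7.8.2 sets the stability condition: "This protocol allows concomitant treatment with anti-parkinsonian medications at stable doses for 4 weeks or greater prior to screening".

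Protocol 9.2 then gives OFF-state two meanings. Subjects on medication are rated after stopping it for 12 hours. For the others, "For patients who are not on any Parkinson's disease SOC, their natural state will be considered OFF-state", and the protocol adds that they have no ON-state. Concurrent medication is collected at screening (Protocol 9.1), so the status is known before allocation.

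The analysis does not use it:

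- **Randomization.** Under Protocol 6.1, subjects "will be randomly assigned to the active and placebo treatment groups at 1:1:1 ratio". No stratification factor is stated.
- **Primary model.** SAP 8.3.7: "The model will include treatment, timepoint, treatment-by-timepoint interaction as the fixed effects and baseline as the covariate". SAP 8.3.3 gives the same model for the other continuous endpoints, and SAP 8.7 repeats it: "Baseline value will be used as a covariate in the MMRM analyses for the primary efficacy endpoint".
- **Baseline table.** SAP 8.3.6 lists demographics, tobacco and alcohol use, and time since diagnosis, but not medication status.
- **Subgroups.** SAP 8.8: "No subgroup analyses are planned for this study".
- **Medication outputs.** SAP 8.3.11 summarizes prior and concomitant drugs by arm, ATC class and preferred term. SAP 8.3.11.3 adds a listing of anti-parkinsonian drugs.

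**The concern.** Two subjects can have the same baseline Part II score, one after a drug withdrawal and one in an everyday state. The protocol draws this distinction, but the model treats the two as exchangeable once their scores match. If their expected six-month change differs, that difference stays in the error term, although the data to remove it have been collected.

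The second issue is interpretability and depends on no assumed effect size. As planned, a reader of the report could not tell whether a Part II difference arose in medicated subjects, unmedicated subjects or both. Nor would the baseline table show how many subjects in each arm were on no anti-parkinsonian drug.

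**Working it through.** **Inputs from the documents.** 174 per arm, difference 3, SD 8, two-sided alpha 0.025, stated power 90% (SAP 8.10.2). Four post-baseline visits (SAP 8.3.3).

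**Inputs assumed.** The documents give neither the unmedicated share p nor the residual effect g (the difference in Month 6 change between the two groups at equal baseline score). I take p = 10% to 50% and g = 1 to 3 points. I treat the SD of 8 as the SD of change after adjustment for baseline score.

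**Step 1: the plan's own figure.** SE = 8 × √(2/174) = 0.858. By the normal approximation, power = Φ(3/0.858 − 2.241) = 89.6%; the noncentral t gives 89.3%. Exactly 90% needs 177 per arm. The stated figure reproduces.

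**Step 2: adding status.** Share of variance explained: R² = p(1−p)g²/64. The SD becomes 8√(1−R²), and power is recomputed at 174 per arm (89.55% without the term). The last two columns show a chance imbalance in the unmedicated share at the 95% limit, 1.96 × √(2p(1−p)/174), and the shift it produces, which is that imbalance times g.

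| p | g | R² | Power with status | 95% imbalance | Shift (points) |
|---|---|---|---|---|---|
| 10% | 1 | 0.14% | 89.60% | 6.3 pp | 0.06 |
| 10% | 3 | 1.27% | 89.95% | 6.3 pp | 0.19 |
| 20% | 2 | 1.00% | 89.87% | 8.4 pp | 0.17 |
| 30% | 3 | 2.95% | 90.48% | 9.6 pp | 0.29 |
| 50% | 1 | 0.39% | 89.67% | 10.5 pp | 0.11 |
| 50% | 3 | 3.52% | 90.65% | 10.5 pp | 0.32 |

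The gain runs from 0.05 to 1.1 percentage points. An R² of 5% would give 91.1% and one of 10% would give 92.6%. Even at p = 50%, where R² is largest for a given g, an R² of 5% needs g = √(0.05 × 64/0.25) = 3.6 points, which is more than the treatment difference the trial is powered for.

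**Step 3: the imbalance shift is not an extra error.** Its SD is g√(2p(1−p)/174). Divided by the SE, 8√(2/174), this is g√(p(1−p))/8 = √R². The shift is therefore the variance loss of Step 2 in other units, and the unadjusted standard error and confidence interval already contain it.

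**Step 4: validity by simulation.** Month 6 ANCOVA with and without status, 174 per arm, 6,000 replicates per scenario and hypothesis. Assumed: baseline SD 6, baseline slope −0.3, unmedicated subjects 4 points lower at baseline.

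| p | g | Power without status | Power with status |
|---|---|---|---|
| 20% | 0 | 90.0% | 90.1% |
| 20% | 2 | 89.4% | 89.6% |
| 30% | 3 | 89.4% | 90.3% |

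Without the status term, the mean error was at most 0.015 points and the type I error 2.3% to 2.6% against a nominal 2.5%.

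**The case against.** The strongest reply is that adjusting for the baseline score alone is a complete, prespecified and valid analysis. The same efficiency argument could be made for Hoehn and Yahr stage, age or time since diagnosis, and nothing in the documents shows that medication status is more prognostic than these. That stands as far as precision goes. What sets medication status apart is that the protocol itself makes the meaning of the OFF score depend on it.

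A second reply is that SAP 8.3.11 already reports medication by arm and class. This is partly right: background therapy will be visible by class. But counts per drug or class do not give the number of subjects on none, because one subject can appear under several. The summary table as described separates prior from concomitant use, not drugs in use at first dose from drugs started later. It shows no efficacy result by status.

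A third reply concerns the remedy. A single status term in a four-visit model estimates one common shift and need not capture a difference at Month 6. This is correct, and the interaction with visit is needed. Nor can a baseline term deal with anti-parkinsonian therapy started during the trial. That is a post-baseline event, and Protocol 9.3 and 9.5 still call for the 12-hour withdrawal before later efficacy visits.

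**Conclusion.** The omission is real and the remedy is free, but the benefit is modest: an efficiency and reporting improvement, not a correction of an invalid analysis. For the assumed range, status explains about 0.1% to 3.5% of the variance and adds at most about 1 percentage point of power. If status predicts nothing beyond the baseline score, essentially nothing is lost by leaving it out or by including it. The reporting gap holds whatever the effect size.

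Three stronger readings are tempting, and the documents do not support them:

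- **That the treatment estimate is biased or the type I error inflated.** Treatment is randomized, and the simulation shows neither.
- **That chance imbalance in status goes uncorrected, or adds bias on top of the lost precision.** The baseline covariate removes the part acting through baseline Part II. The remainder is random error already inside the confidence interval (Step 3).
- **That precision is certainly being lost.** No section says that status predicts change in Part II beyond the baseline score, and none gives the share of subjects on no medication.

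**What to change.** Make these changes before unblinding, since the same adjustment chosen afterwards would look data-driven:

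1. In SAP 8.3.3, 8.3.7 and 8.7, add baseline anti-parkinsonian medication status (on / not on at first dose) and its interaction with visit to the MMRM for Part II and for the MDS-UPDRS secondary endpoints (Part II+III, Part III and total score). The status can be built from the SAP 8.3.11.3 category for drugs started before first dose and still in use.
2. In SAP 8.3.6, add a yes/no row for this status by arm, supplementing the class-level summary in SAP 8.3.11.
3. Report the Month 6 Part II difference, active minus placebo, within each status with confidence intervals and without testing. Amend SAP 8.8 to say so. These intervals will be wide. If 20% are unmedicated (about 35 per arm), the 95% half-width is 1.96 × 8 × √(2/35) = 3.7 points, against 1.96 × 8 × √(2/139) = 1.9 points in the medicated group. The display describes the data and cannot establish a difference between the groups.

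The cost is SAP wording, some programming and about four degrees of freedom (one for status, three for its interaction with four visits), which is trivial with 522 subjects. It needs no new data or visits and no change in clinical management.

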#### 8.8 Examination of Subgroups

No subgroup analyses are planned for this study.

#### 8.9 Handling of Dropouts, Intercurrent Events, and Missing Data

In case of incomplete dates, the following approach will be used:

- If only the day is missing and the month and year are different from the month and year of the index date, the day will be imputed with 1. In case the month and year are the same as the index day the missing day will be imputed with the last day of the month.
- In case of missing months, they will be imputed
  - with July if the year is not the same as the year of the index date
  - with the following month as the month of the index date if the year is the same as the year of the index date.

If not indicated otherwise in case of completely missing dates no imputation will be done.

The MMRM analysis of the primary endpoint assumes that data are missing at random (MAR). The analysis will be conducted in ITT set and subjects will be analyzed as randomized. ITT subjects discontinue from the study for any reason without completing the study are considered intercurrent events. To assess the robustness of this MAR assumption, a conservative control-based multiple imputation method based on missing not at random (MNAR) assumption will be applied to impute missing data arising from intercurrent events for the primary endpoint analysis. In this MNAR approach, subjects who do not complete the study, missing data will be imputed by observed data obtained from the placebo group using multiple imputation with Markov Chain Monte Carlo (MCMC) simulation

method for each treatment separately. The variables for the imputation model will include MDS-UPDRS Part II score at baseline, Month 1, Month 2, Month 3, and Month 6. Approximately 50 datasets will be imputed and the same MMRM analysis as the one applied to the primary analysis will be fitted. The ROUND, MINIMUM and MAXIMUM options will be utilized to ensure imputed values are clinically plausible integers (0 – 52). The results from these 50 analyses will be combined using Rubin's rule to construct the treatment estimates from the parameter estimates and associated standard errors. The difference of the treatment means (active minus placebo) will be presented with the associated standard error and two-sided 95% confidence interval. A random seed number will be selected for the multiple imputation procedure and will be retained.

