6.8. Analysis of Primary Endpoint

The primary endpoint is the change from baseline to Month 6 in of MDS-UPDRS Part II scores. The primary endpoint will be analyzed via a mixed model for repeated measures (MMRM). The model will include treatment, timepoint, treatment-by-timepoint interaction as the fixed effects

and baseline MDS-UPDRS Part II as the covariate. The covariate will assume to be unstructured. The treatment effects and the differences of the treatment effects will be estimated. The two-sided 95% confidence intervals of the treatment differences will be presented.

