Treatment comparisons (10 mg vs. Placebo / 20 mg vs. Placebo) will be carried out by means of the contrasts on the treatment factor by visit effect in SAS® Software, using proc mixed. Treatment effects will be estimated by means of Least Square Means (LSM) and 95% CI. Differences between treatments (10 mg – Placebo / 20 mg – Placebo) will be estimated and resulting 2-sided p-values and associated 95% CI will be presented.

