#### 8.10.2 Clarifications Based on Food and Drug Administration (FDA)'s Feedback

The interim analysis for sample size re-estimation has been completed in March 2023. Based on the interim analysis results and sample size re-estimation decision rules, the results of the interim analysis suggested to increase the sample size to 180 randomized subjects per arm. As of June 9, 2023, the study has completed enrollment with a total sample size of 522 (174 per arm) subjects.

The original evaluable sample size was 120 per arm, and a 20% drop out rate was assumed, which rendered to a sample size of 150 randomized subjects per arm (120/0.8=150). Based on the blinded data review, we noticed a low dropout rate of approximately 6%. With this dropout rate, 180 per arm randomized subjects will lead to 170 (180\*0.94) evaluable subjects per arm, which is around 42% increase from originally calculated sample size of 120 per arm (170/120=1.42). The sample size increased was considered reasonably small (42%) based on the Metha and Pocock (2011) paper that the overall Type I error rate will not be inflated.

The sample size re-estimation for our 3-arm study was handled by the worst-case scenario rules in Table 3 below. The sample size re-estimation method evaluates the conditional power in relationship to a pre-specified decision rule defined by ranges of attainable conditional power values. Only an increase in sample size was possible under this approach if observed conditional power was within the Promising Zone.

Outcome	Worst-case Scenario Approach
Both doses Unfavorable	Study proceeds with originally planned sample size
One dose Unfavorable	Study proceeds with sample size re-estimation increase
One dose Promising	suggested by one dose comparison in Promising Zone
One dose Unfavorable	Study proceeds with originally planned cample size
One dose Favorable	Study proceeds with originally planned sample size
	Study proceeds with larger of the sample size re-
Both doses Promising	estimation increases suggested by two dose comparisons
	in Promising Zone
One dose Promising	Study proceeds with sample size re-estimation increase
One dose Favorable	suggested by one dose comparison in Promising Zone
Both doses Favorable	Study proceeds with originally planned sample size

Table 3. Worst-case Scenario Approach to Sample Size Re-estimation for Multiple Dose Comparisons

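### Does SAP 8.9 leave open whether active-arm dropouts are imputed from placebo data or from their own arm?

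*SAP*

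**What the plan says.** SAP 8.9 takes the primary mixed model for repeated measures to be valid under MAR and sets up one check on it: "a conservative control-based multiple imputation method based on missing not at random (MNAR) assumption will be applied". The next sentence gives the mechanics. For subjects who leave before completing, "missing data will be imputed by observed data obtained from the placebo group using multiple imputation with Markov Chain Monte Carlo (MCMC) simulation", and it continues "method for each treatment separately. The variables for the imputation model will include MDS-UPDRS Part II score at baseline", followed by the scores at Months 1, 2, 3 and 6. Treatment is not among the listed imputation variables.

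About 50 imputed data sets are made, with values rounded and held within 0 to 52. Each is analysed with the primary model and the results are combined by Rubin's rule. The output is an estimate only: "The difference of the treatment means (active minus placebo) will be presented with the associated standard error and two-sided 95% confidence interval". No test is attached.

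Two other places bear on the reading. SAP 8.3.3 fixes the comparisons: "Treatment comparisons (10 mg vs. Placebo / 20 mg vs. Placebo) will be carried out by means of the contrasts". SAP 8.10.2 reports enrolment complete "with a total sample size of 522 (174 per arm) subjects" and a dropout rate of roughly 6% from blinded review. Protocol 6.8 does not discuss missing data, but Protocol 6.0 leaves detailed analysis rules to the SAP.

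**The concern.** One sentence carries two statements that can be set against each other. It names placebo data as the source of imputed values, and it closes by saying the MCMC step is done by treatment, without saying what that means. A programmer who attends only to the closing words might run the procedure with treatment as a BY variable. An MCMC run on the 20 mg arm alone contains no placebo records, so it would impute 20 mg dropouts from 20 mg completers. That is MAR again, reported under a conservative MNAR label.

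This is the only planned departure from MAR. The mITT and per-protocol analyses change the population, not the missing-data assumption. Two programmers could in principle produce different results from the same text, and a choice made after unblinding would be made with the results in view.

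**Working it through.** **Step 1. Set the readings against the text.**

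| Reading | Placebo as source | Control-based, MNAR, conservative | Done by treatment |
|---|---|---|---|
| Each dose's dropouts imputed from placebo, one run per dose | fits | fits | fits |
| MCMC within each arm, own-arm data | contradicts | contradicts | fits |
| Within-arm filling of intermittent gaps only | does not address | does not address | fits |

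Only the first reading fits every part. The third is also outside the scope of 8.9, which imputes data missing because of study discontinuation. The absence of a treatment variable does not favour the own-arm reading, because a model estimated in placebo subjects has no treatment term.

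**Step 2. Reproduce the plan's own figure.** SAP 8.10.2 gives 174 per arm, difference 3, SD 8 and two-sided alpha 0.025. The SE is 8 × √(2/174) = 0.858. Then 3/0.858 − 2.241 = 1.256, which gives power 0.896 (0.893 by noncentral t), against the stated 90%. It reproduces.

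**Step 3. Size of a miscoding.** Placebo dropouts are imputed from placebo data under both codings, so only active-arm dropouts matter. In large samples:

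gap = d × average over last scored visit k of [D₆ − b_k′(D₀,…,D_k)]

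Here d is the dropout proportion, D the treatment difference by visit, and b_k the regression of the Month 6 score on scores up to visit k. The SD cancels. From the SAP, d = 0.06 and D₆ = 3. Two inputs are assumptions not in the documents: visit correlation a·exp(−b × months), set to 0.80 at 1 month and 0.50 at 6 months, and dropouts spread evenly over last scored visit.

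| Effect shape | Bracket for last score at baseline, M1, M2, M3 | Average | × 0.06 |
|---|---|---|---|
| Linear to Month 6 | 3.00, 2.79, 2.49, 2.09 | 2.59 | 0.156 |
| Complete by Month 3 | 3.00, 2.59, 1.97, 1.18 | 2.18 | 0.131 |
| Complete from Month 1 | 3.00, 1.76, 1.23, 0.92 | 1.73 | 0.104 |

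The ceiling, with every dropout last scored at baseline, is 0.06 × 3 = 0.18. With 1-month/6-month correlations from 0.70/0.30 to 0.90/0.80 and even timing, the range is 0.087 to 0.161. Varying dropout timing as well gives 0.03 to 0.18.

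Against the SE: 0.104/0.858 = 0.12, 0.156/0.858 = 0.18, and at the ceiling 0.18/0.858 = 0.21.

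**Step 4. Do the placebo-based versions differ among themselves?** Simulation of 600 three-arm trials per effect shape: 174 per arm, change SD 8, assumed baseline mean 20, 6% random dropout, 50 imputations, rounding and 0–52 bounds, unstructured mixed model, Rubin's rule.

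| Shape | Own arm | Placebo only | Dose pooled with placebo |
|---|---|---|---|
| Linear | −2.958 | −2.804 | −2.804 |
| Complete from Month 1 | −2.957 | −2.855 | −2.861 |

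The gap between own-arm and placebo-only is 0.154 and 0.102 (Monte Carlo SE 0.003), in agreement with Step 3. A second simulation with constant within-subject correlation (0.5 or 0.8), a benefit growing over time and a Month 6 ANCOVA gave 0.16 at 6% dropout.

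**Step 5. How many subjects.** Active-arm dropouts number about 348 × 0.06 = 20.9, or 21, if dropout is equal across arms and none has a Month 6 score. If, as an assumption, 20% of them leave after Month 5 and so have the full End of Trial visit (SAP Appendix 1, footnote e), the number is 20.9 × 0.8 = 16.7, or 17.

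**The case for a change.** The strongest case for a change is that this is the only check on MAR, its purpose fails completely if it is coded within arm, and settling the words before unblinding costs one sentence. The 6% figure comes from a blinded review. At the 20% originally assumed, the second simulation puts the gap at 0.54 to 0.55 points, which is not trivial.

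What stands is that the closing phrase is undefined and that it could be miscoded. What does not stand is that the SAP fails to name the data. It names them in the main clause, and the preceding sentence characterises the method in terms that own-arm imputation cannot meet. Coding it within arm is a misreading of the sentence as a whole, not its literal sense. The 20% rate was a planning assumption that the SAP itself reports as superseded by a much lower observed rate.

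A fuller rewrite would also go past the ambiguity. Adding a step for intermittent gaps, or replacing the specified MCMC with visit-by-visit regression, are design preferences. They do not correct an error.

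**Conclusion.** No change to the plan is called for. Read as a whole, SAP 8.9 imputes dropouts from placebo data, dose by dose, and following it gives a sound control-based estimate. The placebo-based ways of coding it agree to within 0.01 points in simulation.

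Only a coding that overrides the named source would differ, by about 0.10 to 0.16 points on a true difference of 3 and by no more than 0.18. These figures rest on 6% dropout equal across arms and, for the narrower range, on assumed visit correlations and even dropout timing; relaxing those two gives 0.03 to 0.18. The gap grows in proportion to dropout, so a much higher final rate would enlarge it. It would still be confined to a sensitivity estimate with no test attached. The primary analysis, the power and the multiplicity procedure do not depend on it.

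The phrase is a missing detail of the kind that analysts settle correctly when they specify the imputation program.
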